Summary Table of Study Protocol

Title	Evaluation of Long-term Safety in Paediatric Patients With B-precursor Acute Lymphoblastic Leukemia (ALL) who Have Been Treated With Either Blinatumomab or Chemotherapy, Followed by
Protocol version identifier	Transplantation
Date of last version of the protocol	13 November 2018
EU Post Authorization Study (PAS) Register No	TBD
Active Substance	Blinatumomab
Medicinal Product	Blincyto®
Product Reference	
Procedure Number	
Joint PASS	No
Research Question and Objectives	 The overarching aim of this study is to describe the long-term safety profile of B-precursor ALL paediatric patients who have been treated with blinatumomab or chemotherapy prior to undergoing haemopoietic stem cell transplant. Primary Objective To estimate incidence of neuropsychomotor developmental impairment, endocrine impairment, neurological impairment, and immune system impairment (including autoimmune disorders and vaccine failure) Secondary Objectives To estimate the incidence of Haemopoietic Stem Cell Transplant (HSCT) related adverse events (AEs) To estimate the incidence of subsequent relapse of leukemia including in the central nervous system (CNS) To estimate the cumulative incidence of long-term AEs To estimate the incidence of secondary malignant formation
Countries of Study	Europe, Israel, Australia, Brazil, Canada, Mexico, United States

Author	PPD
	Manager, Centre for Observational Research
	Amgen Limited, [name]
	[name]
	Email: PPD
	PPD
	Senior Manager, Centre for Observational Research
	[name]
	[name]
	Email: PPD
	PPD
	Clinical Research Medical Director
	[name]
	[name]
	Phone: PPD
	Email: PPD

Marketing Authorization Holder

Marketing authorization holder(s)	Amgen Inc
MAH Contact	[name]
	[name]
	[name]
	[name]
	[contact]
	[contact]

Confidentiality Notice

This document contains confidential information of Amgen Inc.

This document must not be disclosed to anyone other than the site study staff and members of the Institutional Review Board/Independent Ethics Committee/Institutional Scientific Review Board or equivalent, as applicable.

The information in this document cannot be used for any purpose other than the evaluation or conduct of the research without the prior written consent of Amgen Inc.

Appendix F.	Criteria and Definitions for Disease Status Assessment	68

AEC	Absolute Eosinophil Count
ALL	Acute Lymphoblastic Leukemia
alloHSCT	Allogenic Stem Cell Transplant
BITE	Bispecific T Cell Engagers
BOOP	Bronchiolitis Obliterans Organizing Pneumonia
BRIEF	Behavior Rating Inventory of Executive Function
CI	Confidence Interval
CMV	Cytomegalovirus
CNS	Central Nervous System
CR	Complete Remission
CRS	Cytotoxic Release Syndrome
CTL	Cytotoxic T Lymphocyte
DLCO	Carbon monoxide diffusion capacity
EBMT	European Society for Blood and Marrow Transplantation
EBV	Epstein Barr Virus
eCRF	Electronic Case Report Form
EDC	Electronic Data Capture (system)
EFS	Event Free Survival
EMA	European Medicines Agency
EU	European Union
FDA	Food and Drugs Agency
FEV 1	Forced Expiratory Volume in 1 second
FSH	Follicle Stimulating Hormone
GvHD	Graft versus Host Disease
GVP	Good Pharmacovigilance Practice
HPA	Hypothalamus-Pituitary-Adrenal
HSCT	Haemopoietic Stem Cell Transplant
ICJME	International Committee of Medical Journal Editors
IEC	Independent Ethics Committee
IRB	Institutional Review Board
IRT	Interactive Response Technology
IUGR	Intrauterine Growth Restriction
IV	Intravenous
KM	Kaplan-Meir (analysis/curve)
LH	Lutenizing Hormone
LV-SF	Left Ventricular Systolic Function
MEF25	25% of forced vital capacity
MRD	Minimal Residual Disease
MRD positivity	MRD at a level $\geq 10^{-4}$ in PCR and/or flow quantification

2. List of Abbreviations

MTX	Methotrexate
NIH	National Institute of Health
OS	Overall Survival
PASS	Post Authorization Safety Study
PCR	Polymerase Chain Reaction
Ph-	Philadelphia Chromosome Negative
PRAC	Pharmacovigilance Risk Assessment Committee
PSUR	Periodic Safety Update Report
S-GOT	Serum Glutamic Pyruvic Transaminase
S-GPT	Glutamic Pyruvic Transaminase
SOC	Standard of Care
SOP	Standard Operating Procedure
WBC	White Blood Cells

3.	Responsible Parties	
PPD	, Amgen Ltd, UK	
PPD	, Amgen Inc, US	
PPD	, Amgen Inc, US	

- 4. Abstract
- Study Title

Evaluation of Long-Term Safety in Paediatric Patients with B-Precursor Acute Lymphoblastic Leukemia (ALL) who have been treated with either Blinatumomab or Chemotherapy, followed by Transplantation

• Study Background and Rationale

Paediatric acute lymphoblastic leukemia (ALL) is a hematologic malignancy characterized by the proliferation of immature and abnormal lymphoid cells in the bone marrow and peripheral blood. ALL is the most common cancer diagnosed in children with an incidence of about 4 per 100,000 children per year

(International-Berlin-Frankfurt-Muenster study group [I-BFM SG], 2010). B-precursor ALL is an aggressive malignant disease. Based on the fact that most agents are associated with considerable toxicity and the lack of novel treatment options for patients who relapse or are refractory to treatment, additional, and innovative therapeutic approaches are urgently needed.

Blinatumomab (Blincyto[®]) belongs to a new class of bispecific antibody constructs called bispecific T cell engagers (BITE[®]). This T cell–mediated target-specific killing is the therapeutic mechanism of action of blinatumomab (Löffler et al, 2000; Wolf et al, 2005).

Blinatumomab specifically targets cells that express CD19, a marker solely expressed by B cells, including B-precursor ALL cells. Due to its unique ability to redirect T cells via CD3 towards a CD19⁺ tumor cell lysis, blinatumomab can elicit repeated target cell elimination by cytotoxic T cells and a polyclonal response of previously primed CD4⁺ and C8⁺ T cells.

Blinatumomab received accelerated approval from the Food and Drugs Agency (FDA) for the treatments of adults and children with relapsed/refractory Philadelphia chromosome negative (Ph-) B-cell ALL in 2014: this was converted to full approval in 2017. The European Medicines Agency (EMA) granted conditional approval to blinatumomab for the treatment of adults with relapsed/refractory Ph- B-cell ALL in November 2015, with conditional approval converted to full approval in June 2018. Blinatumomab is indicated as monotherapy for the treatment of paediatric patients aged 1 year or older with Ph- CD19 positive B-cell precursor ALL which is refractory or in relapse after receiving at least 2 prior therapies or in relapse after receiving prior allogeneic hematopoietic stem cell transplantation (alloHSCT).

This study (Study 20180130) will provide the opportunity to investigate the long-term safety profile in paediatric patients with respect to known short-term toxicities of blinatumomab, eg, those related to the immune, neurologic, and HSCT-related events. The study will involve long-term follow-up of both chemotherapy- and blinatumomab-treated paediatric patients who then undergo alloHSCT. Patients who have undergone alloHSCT following treatment with either blinatumomab or standard of care (SOC) chemotherapy will be invited to participate in the 20180130 study.

Study 20180130 will provide the opportunity to investigate the long-term safety profile of blinatumomab, by providing 12 years of follow-up of patients treated with either blinatumomab or chemotherapy, followed by alloHSCT (follow-up commencing at transplantation). The study will investigate neuropsychomotor developmental impairment, endocrine impairment, neurological impairment, and immune system impairment.

- Research Question and Objective(s)
 - Primary Objective

(1) To estimate incidence of neuropsychomotor developmental impairment, endocrine impairment, neurological impairment, and immune system impairment (including auto-immune disorders and vaccine failure)

- Secondary Objectives
 - (1) To estimate the incidence of HSCT related adverse events (AEs)
 - (2) To estimate the incidence of subsequent relapse of leukemia including in the CNS
 - (3) To estimate the cumulative incidence of long-term AEs
 - (4) To estimate the incidence of secondary malignant formation
 - (5) To estimate overall survival
- Hypothesis Estimation
 - The study will compare blinatumomab therapy versus chemotherapy treatment

for the occurrence of neuropsychomotor developmental impairment, neurological impairment, endocrine impairment, and immune system impairment.

• Study Design/Type

This study is a prospective observational study.

• Study Population or Data Resource

Paediatric patients who have undergone alloHSCT following treatment with either blinatumomab or SOC chemotherapy will be invited to participate in the study.

• Summary of Patient Eligibility Criteria

Inclusion Criteria

Paediatric B-precursor ALL patients with any indication world-wide that received blinatumomab or chemotherapy in routine clinical practice, followed by transplantation, or European Union (EU) paediatric indications that may be authorized in the future. This means that paediatric patients which receive blinatumomab off-label in the EU or with a different indication in ex-EU regions may be included in the study.

Patient's legally acceptable representative has provided informed consent when the patient is legally too young to provide informed consent and the patient has provided written assent based on local regulations and/or guidelines prior to any study-specific activities/procedures being initiated.

Exclusion Criteria

N/A

Follow-up

Enrolment of patients into 20180130 will occur if they meet all eligibility criteria. Patients will be followed for a maximum of a 12-year period or up to the age of 25 years, death, withdrawal of consent, or loss to follow-up, whichever comes first. The study will end when the 12-year follow-up period on the last patient enrolled in the study is completed. If the last patient enrolled on study dies or is lost to follow-up before the 12 years following alloHSCT, the remainder of the patients on study will

continue to be followed until all patients on study have reached 12 years following alloHSCT, until death, withdrawal of consent, or lost to follow-up, whichever comes first. All treatments for ALL will be captured in this period.

Data will be recorded in an eCRF and will encompass information abstracted from patient charts from routine clinical visits. Data abstraction will be performed approximately every 6 months (± 30 days) from enrolment. Additional data on neuropsychomotor development will be assessed through specific questionnaires (paper and/or electronic) which will be administered at pre-specified intervals (approximately every 6 months [± 30 days] from enrolment for patients up to 6 years old and approximately yearly [± 60 days] for patients from 6 years old).

• Variables

Outcome Variables
 Impairment defined as any of the following:

- Neuropsychomotor development impairment in any area of social and emotional, language/communication, cognitive, or motor
- Neurologic impairment defined as any peripheral nervous system disorders including neuromuscular junction disorders and central nervous system disorders
- Endocrine impairment defined as any
 Hypothalamus-Pituitary-Gonadal Axis disorders,
 Hypothalamus-Pituitary-Adrenal (HPA) Axis disorders,
 Hypothalamus-Pituitary-GH Axis disorders,
 Hypothalamus-Pituitary-Thyroid Axis disorders
- Immune system impairment defined as any leukopenia (neutropenia and/or lymphopenia); low IgG; low IgM, and; low IgA; autoimmune disorders; vaccination failure

HSCT-related AE defined as any second malignancy; Graft versus Host Disease (GvHD); infection, and/or; relapse

Relapse is defined as any of the following:

- Isolated bone marrow relapse (M3¹ in the absence of extramedullary involvement)
- Combined bone marrow response (M2 or M3 marrow and at any extramedullary manifestation of ALL)
- Extramedullary relapse (either CNS relapse, testicular relapse, or relapse at other sites²)

AE in any of the following organ systems: gastrointestinal, hematologic, dermatology, cardiac, pulmonary, hepatic, renal, neurological, infection, immunology, and skeletal

Secondary malignancy: tumor type and anatomical site of tumor

Overall survival as time from transplant until death

¹ Cytological bone marrow assessment grading: see Appendix F for details

² See appendix F for relapse criteria (including extramedullary relapse)

Covariates

Demographics and clinical characteristics including comorbidity Recording of ALL-related diagnoses history both prior to and following blinatumomab/SOC chemotherapy

- Disease status (prior to blinatumomab/SOC chemotherapy)
- Minimal residual disease (MRD) status (following treatment);
 MRD positivity defined at a level ≥ 10⁻⁴ in polymerase chain reaction (PCR) and/or flow quantification
- Relapse (following treatment)
 - Time point of relapse (time since primary diagnosis and time after completion of primary therapy)
 - Whether extramedullary relapse
 - Bone marrow status at relapse
- Secondary malignancy (following treatment)

Recording of ALL-related treatment history

- Details of SOC-chemotherapy therapy: specific therapy, and; duration of therapy
- Details of blinatumomab therapy: number of cycles; occurrence of further blinatumomab therapy following initial discontinuation, and; duration of therapy

Recording of alloHSCT status

- Occurrence of alloHSCT(s)
 - Interval between SOC-chemotherapy/blinatumomab and alloHSCT

Clinically relevant events prior to initiation of SOC/blinatumomab therapy or after initiation of therapy and before alloHSCT

- Neurologic event
- Endocrine event (including evidence of growth delay)
- Immune event
- Toxicity (gastrointestinal, hematologic, dermatologic, cardiac,

pulmonary, hepatic, renal, infection, skeletal, etc.)

Other important clinical factors

- Comorbidity
- Concomitant medication

- Prenatal development
- High-risk pregnancy
- Delivery complications including hypoxia
- Gestational time at the delivery
- APGAR score
- Gestational weight (IUGR)
- Psychomotor development impairment and psychiatric conditions recognised prior to the therapy
- Pregnancy and breastfeeding status after blinatumomab initiation
- Study Sample Size

The targeted sample size for this study is approximately 298 patients. However, the actual number of patients that will be included in the study will depend on the results of site feasibility, willingness of patients (or their legal guardians/caregiver) or sites to participate in the study.

• Data Analysis

Continuous variables will be summarized by mean, median, standard deviation, lower and upper quartiles, and minimum and maximum values. Categorical variables will be summarized by number and percentage of patients in each category. For categorical outcomes, 95% confidence intervals (CIs) will also be presented where appropriate. For time-to-event endpoints, Kaplan-Meier (KM) curves and KM proportions at select time points, the numbers of patients with events and then number of patients censored will be used to summarize the data.

A comparison between the blinatumomab versus chemotherapy group will be conducted at the final follow-up in the study pending adequate sample size is enrolled (\geq 50 patients per arm) and the blinatumomab and SOC groups are comparable (eg, there is overlap between PS distributions across the two groups, or no critical differences that cannot be accounted/adjusted for). Prior to comparison being conducted, covariates listed in Section 9.3.2 will be evaluated for differences between the two groups. Any covariates that are not comparable between the two (Wald chi-square or t-test, p-value < 0.25), will be evaluated as a covariate for adjustment in the models. A multivariate logistic regression will be used to compare incidence event objectives and Cox regression will be used to compare time-to-event objectives. Also, we will conduct a propensity score weighting analysis based on the covariates collected for this study.

This study will have 5 interim analyses, taken at 2-year intervals over the course of the 12-year follow-up. A final report will be produced at the end of the study.

5. Amendments and Updates

None.

6. Milestones

For the timely sharing of the collected data, enrolment updates will be given with each periodic safety update report (PSUR), and analysis of interim data will be performed at 2-year intervals and reported through the respective timetable defined as per regulatory requirements.

After the last data collection has been completed, a final data analysis will be performed and a final report summarizing the results of the study will be completed and submitted to Regulatory Agencies as appropriate within 12 months after end of data collection (ie, when 12-year follow-up is completed on the last patient enrolled in the study), and will be prepared regardless whether the study is completed or prematurely terminated.

This study will have a follow-up up to twelve years. Milestone dates are approximate and can shift based on study start and local approval timelines.

Milestone	Planned date
Start of data collection	Approximately Q2 2020
End of data collection	Approximately Q3 2037
Interim Analysis	Every 2 years from the start of data collection
Final report of study results	Approximately Q3 2038

7. Rationale and Background

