9.2.1 Study Period

Enrolment of patients into 20180130 will occur if they meet all eligibility criteria. All eligible patients or their caregivers/legal guardians will be approached to provide informed consent for participation. Once informed consent has been given, and all inclusion/exclusion criteria are met, the patient will be enrolled via interactive response technology (IRT) in the study and data collection will begin. The study will commence at the first data collection of the first site. Patients will be followed for a maximum of a 12-year period or up to the age of 25 years, death, withdrawal of consent, or loss to follow-up, whichever comes first. The study will end when 12 years of follow-up for the last patient (if the patient has not withdrawn consent, been lost to follow-up, or died before the end of the 12 years of follow-up) is completed. If the last patient enrolled on study dies or is lost to follow-up before the 12 years following alloHSCT, the remainder

of the patients on study will continue to be followed until all patients on study have reached 12 years following alloHSCT, until death, withdrawal of consent, or lost to follow-up, whichever occurs first.

Data will be entered into an eCRF and will encompass information abstracted from patient charts from routine clinical visits. Data abstraction will be performed approximately every 6 months (± 30 days) starting at enrolment. Additional data on neuropsychomotor development will be assessed through specific questionnaires (paper and/or electronic) which will be administered at pre-specified intervals starting at enrolment (approximately every 6 months [± 30 days] for patients up to 6 years old and approximately yearly [± 60 days] for patients from 6 years old).

The first day of follow-up (day 1) will be the date of successful completion of alloHSCT (following chemotherapy/ blinatumomab treatment).

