9.2.5 Study Follow-up

This is a prospective study where data will be collected at routine clinical visits which will occur per standard of care (for a period of up to 12 years). A total of 12 years follow-up or 144 months of follow-up is planned for study 20180130. At each data collection stage, relevant information will be retrieved from patient charts subsequent to the preceding data abstraction time point to ensure there is no gap in data collection. Data abstraction will be performed approximately every 6 months (± 30 days) starting at enrolment. Additional data on neuropsychomotor development will be assessed through specific questionnaires (paper and/or electronic) which will be administered at pre-specified intervals starting from enrolment (approximately every 6 months [± 30 days] for patients up to 6 years old and approximately yearly [± 60 days] for patients from 6 years old). For each enrolled patient, data collection will end at 12-years of follow-up, the age of 25 years, loss-to-follow-up, withdrawal of consent, or death, whichever occurs earliest. All treatments for ALL will be captured in this period.

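### The study-end rule is tied to the last patient enrolled although follow-up runs from transplant, so read literally it can close the study early and, in some cases, leaves the end undefined

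*Protocol*

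**What the plan says.** Time zero is the transplant. The Abstract has "follow-up commencing at transplantation", and Section 9.2.1 has "The first day of follow-up (day 1) will be the date of successful completion of alloHSCT". Patients are invited after alloHSCT, and neither the inclusion criteria (9.2.3.1) nor the exclusion criteria (9.2.3.2, none) limit how long after.

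The individual stop is stated in the Abstract and 9.2.1 as "Patients will be followed for a maximum of a 12-year period or up to the age of 25 years", with death, withdrawal and loss to follow-up as the other ends. Section 9.2.5 gives it per patient: "data collection will end at 12-years of follow-up, the age of 25 years, loss-to-follow-up, withdrawal of consent, or death", whichever is earliest. Section 9.6 also includes age 25.

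The study-level rule in the Abstract is "The study will end when the 12-year follow-up period on the last patient enrolled in the study is completed". Section 9.2.1 has the same rule with a proviso: "if the patient has not withdrawn consent, been lost to follow-up, or died before the end of the 12 years of follow-up". Sections 6 and 13 define the end of data collection in the same way, by the last patient enrolled.

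Both the Abstract and 9.2.1 then add a continuation sentence. Its condition is "If the last patient enrolled on study dies or is lost to follow-up before the 12 years following alloHSCT". Its consequence is that the remaining patients "continue to be followed until all patients on study have reached 12 years following alloHSCT, until death, withdrawal of consent, or lost to follow-up". Age 25 is in neither the condition nor the consequence.

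**The concern.** The rule counts 12 years from one event (transplant) but picks the patient who closes the study by another (enrolment). The two orderings agree only if the interval between the events is much the same for everyone, and nothing in the protocol ensures that. If they differ, the last-enrolled patient can finish first, and the continuation sentence does not cover that case.

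The follow-up at risk is the latest part for the most recently transplanted patients. This is a category 1 post-authorisation safety study concerned with late outcomes such as secondary malignancy and developmental or endocrine impairment. The same rule sets the end of data collection and starts the 12-month clock for the final report.

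A second, separate defect is that the study-level sentences leave out age 25. A last-enrolled patient who ages out never completes 12 years, and no sentence says when the study then ends.

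**Working it through.** **Inputs from the protocol.** Target 298 patients and 35% long-term survival (9.5). Start of data collection about Q2 2020 and end about Q3 2037 (Section 6). Age under 18 at treatment (7.2). Four recruitment age groups of roughly equal size, the oldest 13–17 years (9.5).

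**Input not in the protocol.** The transplant-to-enrolment interval. The length of enrolment is not stated either. From the milestones, Q2 2020 to Q3 2037 is about 17.25 years, and 17.25 − 12 = 5.25 years (5.0 to 5.5 depending on where in each quarter one counts). That equals the enrolment period only if the last patient enrolled has no interval. The Q3 2037 date can therefore be neither confirmed nor refuted.

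**When the anchor fails.** For patient *i* let *e* be the enrolment date, *g* the interval from transplant to enrolment and *a* the age at transplant. Transplant is at *e − g*, and the patient's own stop, if alive and on study, is *e − g* + min(12, 25 − *a*). With L the last patient enrolled, the study closes at *e*(L) − *g*(L) + 12. A patient young enough to complete 12 years is cut off when

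*g*(L) − *g*(i) > *e*(L) − *e*(i).

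If all intervals are equal, the left side is zero and nobody is cut off.

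**Hand example (assumed intervals).** L enrols at study year 5.25, having been transplanted 3 years earlier, and reaches 12 years at 5.25 − 3 + 12 = 14.25. Another patient is transplanted and enrolled at year 5.0 and is due at 17.0. Loss: 17.0 − 14.25 = 2.75 years.

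**Size by simulation.** Assumptions: 298 patients, enrolment uniform over 5.25 years, interval uniform from 0 to a maximum, equal age groups, and closure at the last-enrolled patient's 12-year date.

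| Maximum interval | Cut off, all stay on study | Cut off, 35% survival and death fallback |
|---|---|---|
| 0 | 0% | 0% |
| 1 year | about 2.5% (7 patients) | about 0.3% (1) |
| 2 years | about 5% (15) | about 0.6% (2) |
| 4 years | about 10% (30) | about 1.2% (4) |

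The last column follows from the middle one. The rule bites only if the last-enrolled patient survives (0.35), and only survivors can lose follow-up (0.35): 0.35 × 0.35 = 0.1225, and 0.1225 × 2.5%, 5% and 10% gives 0.3%, 0.6% and 1.2%. At least one patient is cut off in about 80% to 90% of runs if all stay on study, and in about 23% to 29% with survival and the fallback. Where anyone is cut off, the mean largest loss is about 0.4 years (maximum interval 1 year) to 1.8 years (4 years).

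**Age 25.** Available follow-up is min(12, 25 − *a*): 12 years at age 13, 11 at 14, 10 at 15, 9 at 16, 8 at 17, and about 7 just under 18. Anyone transplanted after the 13th birthday cannot complete 12 years, which is essentially the oldest of the four recruitment groups.

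**What happens to the study end, by the fate of the last-enrolled patient.**

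| Fate | Result on the text |
|---|---|
| Completes 12 years | Study closes, whoever remains |
| Dies or is lost | Others continue |
| Withdraws consent | Proviso in 9.2.1 lifts the end rule, the Abstract has no proviso, and the continuation sentence does not apply: undefined |
| Reaches 25 first | Trigger never met, continuation sentence does not apply: undefined |

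**The case against.** The strongest reply is that the intent is clear. Section 9.2.5 sets the end of data collection for each enrolled patient, the Abstract and 9.2.1 state the 12-year or age-25 limit as a maximum, and a sensible sponsor would not close sites with patients still due. That stands as evidence of intent and is why severity is low. It does not repair the study-level rule, which names a different event and is repeated in the sections that fix the end of data collection and the final report.

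The second reply is that the size rests on intervals the protocol does not give, and that high mortality makes the death fallback likely to apply. Both parts stand. The figures assuming everyone stays on study are an upper illustration. The figures also close the study at the last-enrolled patient's 12-year date even when that patient would have aged out, a case the text leaves undefined, so they lean high.

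Three stronger readings are tempting and not supported:

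- A reader might infer that leaving age 25 out of the continuation sentence lets the study close early. Omitting a stop can only lengthen follow-up. At worst it carries some patients past 25, against the Abstract, 9.2.1, 9.2.5 and 9.6, and it is more naturally read as subject to the stated maximum.
- A reader might infer that the study closes when a last-enrolled adolescent turns 25, for example after 9 years for a patient transplanted at 16, cutting off a large share of the cohort. No sentence says so. The trigger is completed 12-year follow-up, and a patient who ages out has not met it.
- A reader might infer that withdrawal by the last-enrolled patient closes the study. The proviso in 9.2.1 excludes that, although what happens instead is not stated.

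**Conclusion.** The point holds as a wrongly stated rule of low severity. The only literal route to early closure is that the last patient enrolled completes 12 years before a patient who was enrolled earlier but transplanted later. Separately, the study end is undefined if that patient ages out, and incompletely specified if that patient withdraws. The continuation sentence also lacks the age-25 stop applied to every patient elsewhere.

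Under the assumed intervals and the protocol's own survival figure, the expected loss is about 1 to 4 of 298 patients. It is nil if intervals are equal and higher if more patients survive. No firmer size can be given from the documents.

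**What to change.** Reconcile the study-end and continuation sentences in the Abstract and Section 9.2.1 with the per-patient rule already in Section 9.2.5. State once that the study ends when every enrolled patient has reached his or her own stop as listed there, with no reference to the last patient enrolled. Change the matching definitions of the end of data collection in Sections 6 and 13. One such rule removes the anchor problem, the two undefined cases and the age-25 mismatch together.

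The change is wording only. Its cost is that data collection may run slightly past the last-enrolled patient's 12-year date. It is still bounded by 12 years after the last transplant.

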Common study protocol, study status, and report(s) will be included in regulatory communications in line with the risk management plan, PSURs, and other regulatory milestones and requirements. Study progress reports will be produced at 2-year intervals from the initiation of the study throughout the 12-year duration of the study: each progress report will be submitted independently of the PSUR to the agency. A final report will be completed within 1 year after the end of data collection, (ie, when 12-year follow-up is completed on the last patient enrolled in the study), and will be prepared regardless whether the study is completed or prematurely terminated. Both the progress and final reports will be submitted to the EMA and relevant Competent Authorities in participant countries (where this is a local requirement). The final reports will also be shared with all participating HCPs in this study. Any manuscript and/or abstract for scientific presentation(s) will be developed and submitted in accordance in with the 2012 Guideline on Good Pharmacovigilance Practice (GVP): Module VIII – Post-Authorisation Safety Studies (EMA, 2016 module VIII). Similarly, any emerging safety concerns that may be identified during interim analyses will be immediately communicated to all participating physicians and regulatory authorities in accordance with Guideline on Good Pharmacovigilance Practice.

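### The abstract's five interim analyses and Section 13's 12-year study duration contradict Section 6, whose two-yearly schedule over about 17 years of data collection gives about eight

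*Protocol*

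**What the plan says.** Three places in the protocol set the timetable for interim looks.

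- Abstract, Data Analysis: "This study will have 5 interim analyses, taken at 2-year intervals over the course of the 12-year follow-up".
- Section 6 (Milestones): interim analysis is planned as "Every 2 years from the start of data collection". Data collection starts "Approximately Q2 2020" and ends "Approximately Q3 2037", and the final report is due "Approximately Q3 2038". The section calls these dates approximate and able to shift. It gives no number of interims.
- Section 13: progress reports come at 2-year intervals from study initiation, "throughout the 12-year duration of the study".

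Two other places say what the 12 years are. Section 9.2.1 applies them to the individual: "Patients will be followed for a maximum of a 12-year period or up to the age of 25 years". The abstract's follow-up paragraph gives the closing rule: "The study will end when the 12-year follow-up period on the last patient enrolled in the study is completed".

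**The concern.** The abstract and Section 13 appear to treat the per-patient follow-up as the length of the study. Under the closing rule the study runs for the enrolment period plus the last patient's follow-up, and the milestone dates allow for that. Section 13 even conflicts with itself: it gives the study a 12-year duration, then ends data collection when the last enrolled patient completes 12 years.

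The abstract and Section 6 cannot both be followed. This is a post-authorisation commitment to study long-term effects, and Section 7.2 says that effects beyond 3 years are largely unknown. A team working from the abstract or from Section 13 would stop scheduled interim analyses or progress reports years before the data stop arriving. Section 13 also names interim analyses as an occasion when emerging safety concerns may be identified and must be communicated.

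**Working it through.** **Inputs.** Start of data collection Q2 2020, in decimal years 2020.25 to 2020.50. End of data collection Q3 2037, 2037.50 to 2037.75. Spacing 2 years. All are from Section 6. The 12-year figures are from the abstract and Section 13. Section 9.2.1 says the study commences at the first data collection at the first site, so Section 13's study initiation and Section 6's start of data collection are the same point.

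**Step 1: reproduce the abstract's five.** In a 12-year window with the final analysis at year 12, the two-yearly points before the end are years 2, 4, 6, 8 and 10. That is five, so the count is right for a study lasting 12 years.

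**Step 2: length of data collection.**
- Shortest: 2037.50 − 2020.50 = 17.0 years.
- Longest: 2037.75 − 2020.25 = 17.5 years.
- Mid-quarter: 2037.625 − 2020.375 = 17.25 years.

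**Step 3: number of interims under Section 6.** The eighth point is at 8 × 2 = 16 years, inside even the shortest span. A ninth would be at 18 years, outside even the longest. The schedule is 2022, 2024, 2026, 2028, 2030, 2032, 2034 and 2036, which is eight. The answer is the same wherever the dates fall within their quarters.

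**Step 4: gaps if the other wording is followed from the start of data collection.**

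| Wording followed | Last interim or report | Time left to end of data collection |
|---|---|---|
| Abstract: five interims | start + 10 years = Q2 2030 | 17.0 − 10 = 7.0 to 17.5 − 10 = 7.5 years |
| Section 13: 12-year duration | start + 12 years = Q2 2032 | 17.0 − 12 = 5.0 to 17.5 − 12 = 5.5 years |
| Section 6: every 2 years | start + 16 years = Q2 2036 | 17.0 − 16 = 1.0 to 17.5 − 16 = 1.5 years |

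**Step 5: could the dates shift enough to rescue five?** With two-yearly points from the start, a sixth interim becomes due once data collection exceeds 12 years. The planned span would have to shrink by at least 17.0 − 12 = 5.0 years.

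**Step 6: another anchor.** Suppose the 12 years are counted back from the end of data collection, so that they start about 2025.50 to 2025.75. Five interims then fall at about 2027.5, 2029.5, 2031.5, 2033.5 and 2035.5 (each up to a quarter later), and the last is 2.0 years before the end. That avoids the late gap, but it contradicts the anchor in Section 6 and delays the first interim to about 7.0 to 7.5 years after the start.

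**The case against.** The strongest reply is that Section 6 already has the right schedule. It carries no cap, the number five appears in one abstract sentence only, and a team that follows Section 6 has no gap. That stands: the gap arises only if the abstract or Section 13 is followed instead. It does not remove the conflict, because nothing says which text governs.

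A reader might infer that safety review would stop in 2030, or that late effects in later-enrolled patients could not be detected. The protocol does not support that.

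- Section 9.7.1 plans bi-annual data summaries for specified periodic safety update reports, with no stated end.
- Section 11.2 collects safety events after blinatumomab exposure until final study contact, with short reporting deadlines. This covers blinatumomab-exposed patients, not the chemotherapy group.
- A final analysis and report follow the end of data collection.
- Section 13 requires concerns identified at interim analyses to be communicated. It does not make interims the only means of detection.

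These routes do not replace the interims: Section 6 lists interim analysis separately from the enrolment updates given with each periodic report, and Section 13 submits progress reports independently of those reports.

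It is also tempting to say how much follow-up the last-enrolled patient would have by 2030. The protocol states no enrolment period. The 5.0 to 5.5 years beyond 12 is a subtraction between approximate dates, and follow-up counts from transplant, not enrolment. Any such figure is an assumption.

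**Conclusion.** The contradiction holds. The abstract's count and Section 13's study duration fit a 12-year study, while Section 6 and the closing rule describe one of about 17 years. Section 6 gives about eight interims. Following the abstract from the start of data collection would end the interims some 7 years early, and following Section 13 would end progress reports some 5 years early. These figures assume the current milestone dates, which may shift, though no modest shift turns eight into five.

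The consequence is limited to the scheduled interim analyses and progress reports. The comparison of arms is planned only at final follow-up (Section 9.7.2.2.3), so type I error and power are untouched, and no endpoint or sample size changes. The point should still be corrected: this is a long-term safety study, and the texts disagree on how long scheduled interim reporting lasts.

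**What to change.** In the abstract, drop the fixed count of five and the reference to 12-year follow-up. In Section 13, drop the 12-year study duration. In both, say that interim analyses (abstract) and progress reports (Section 13) occur every 2 years from the start of data collection until the end of data collection, about eight on the current planned dates. Give eight only as an approximate figure, since a fixed count would go wrong again if the milestone dates move. Section 6 needs no change.

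The cost is an edit to two sentences and up to 8 − 5 = 3 further descriptive interim reports compared with the abstract, all of which Section 6 already implies.
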